10.3 Analysis Population

Sites will be limited to enrolling 20% (28) of the total sample size. The following populations are defined:

Table 5: Analysis Population List

Population	Description
Enrolled	All participants who sign the ICF will be classified as enrolled.
Intent-to-Treat (ITT)	The intent-to-treat population will consist of all participants into whom has signed the ICF, met all inclusion/exclusion criteria, and the Pristine™ Catheter was placed.
Per-Protocol	A Per-Protocol (PP) population may be created if there are participants who have any major deviations. The PP population will consist of any participants in the ITT population who do not have any major deviations. The deviations that are considered to have a “major” grade will be defined a priori in the SAP.

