10.5 Primary Endpoint

The combined primary endpoint is the overall rate of infectious complications and non-infectious complications requiring revision to maintain patency and improve access performance at 3 months. Based on the DOPPS study data, competitor control devices had an average incidence rate of 31.5 complications per 1000 patient days. To show non-inferiority of the Pristine™ Catheter, a 5 complications per 1000 patient days non-inferiority margin is used to establish a performance goal (PG) of 36.5 events per 1000 patient days.

The analysis of the primary endpoint will be based on the following test of Poisson rate:

H₀: The complication rate through 3 month is greater than or equal to 36.5 events per 1000 patients days at 3 months.

H₁: The complication rate through 3 month is less than 36.5 events per 1000 patient days at 3 months.

That is:

$$\mathbf{H_0: \lambda \geq \lambda_0}$$

$$\mathbf{H_1: \lambda < \lambda_0}$$

Where λ_0 is the PG of 36.5 events per 1000 patient days.

A one-sided p-value will be derived based on an Poisson distribution. The Pristine™ Catheter will be considered to have achieved the primary endpoint objective if the one-sided p-value is less than 0.025.

Conditioned on the success of the above test, a superiority test will be conducted to show that the Pristine™ Catheter is superior to the performance goal. The above test will be repeated with a PG of 31.5 events per 1000 patient days.

The analyses of the primary endpoint will be based on the ITT population and repeated with per-protocol population as sensitivity analyses.

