10.6 Secondary Endpoint(s)

The secondary endpoints will be summarized with descriptive statistics (without formal statistical hypothesis testing) using the ITT population. For categorical variables, summary statistics will include frequency counts and percentages. For continuous variables, summary statistics will include mean, standard deviation, minimum, median, and maximum. CIs (95%) will also be provided.

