## 4 Analysis Population Set(s)

### 4.1 Population Definitions

The following populations are defined:

Table 2: Analysis Population List

Population	Description
Enrolled	All participants who sign the ICF will be classified as enrolled.
Intent-to-Treat (ITT)	
The ITT population will consist of all participants who have signed the ICF, met all inclusion/exclusion criteria, and had the procedure initiated.
 
The ITT population includes the following three groups on the Subject Disposition CRF page: Eligibility met but device not inserted, Device inserted but subject did not undergo first dialysis session, and Treated with study device.

Modified Intent-to-Treat (mITT)	
The mITT population will consist of all ITT participants treated with the study device.
 
The mITT population includes subject treated with study device on the Subject Disposition CRF page.

Per-Protocol (PP)	
A PP population may be created if there are participants who have any major deviations. The PP population will consist of any participants in the mITT population who do not have any major deviations. The deviations that are considered to have a “major” grade will be identified and summarized in Appendix 3 prior to data analyses.

All endpoints will be analyzed primarily based on the mITT population and ITT population where applicable. PP analyses may also be performed for the primary endpoints and will only serve as sensitivity analyses.

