$$\text{Length of investigation duration (Days)} = \text{Discontinuation Date} - \text{Date of index procedure} + 1$$
- If the subject has not experienced any of the above events prior to the 3-months visit date, then the 3 months visit date will be used to calculate the length of investigation duration; in case of subject having the 3 months visit out of window and after day 105 or the subject misses the 3 months visit, then day 105 will be the end date of investigational period.
 
$$\text{Length of investigation duration (Days)} = \min((3 \text{ months visit date} - \text{date of index procedure} + 1), 105 \text{ days})$$

The analysis will be performed on the mITT population and repeated with per-protocol population as sensitivity analyses.

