### 5.2.2 Hypothesis Testing

The primary endpoint is the overall rate of infectious complications and noninfectious complications requiring revision to maintain patency and improve access performance at 3 months. Based on the DOPPS study data, competitor control devices had an average incidence rate of 31.5 complications per 1000 patient days. To show noninferiority of the Pristine™ Catheter, a 5 complications per 1000 patient days non-inferiority margin is used to establish a performance goal (PG) of 36.5 events per 1000 patient days.

The Primary Patency endpoint will be evaluated by the following hypothesis:

$H_0$ : The complication rate through 3 month is greater than or equal to 36.5 events per 1000 patients days at 3 months.

$H_1$ : The complication rate through 3 month is less than 36.5 events per 1000 patient days at 3 months.

That is:

$H_0: \lambda \geq \lambda_0$

$H_1: \lambda < \lambda_0$

Where  $\lambda_0$  is the PG of 36.5 events per 1000 patient days.

A one-sided p-value will be derived based on a Poisson distribution. The Pristine™ Catheter will be considered to have achieved the primary endpoint objective if the one-sided p-value is less than 0.025.

Conditioned on the success of the above test, a superiority test will be conducted to show that the Pristine™ Catheter is superior to the performance goal. The above test will be repeated with a PG of 26.5 events per 1000 patient days.

The analyses of the primary endpoint will be based on the mITT population and repeated with per-protocol population as sensitivity analyses. The analyses will be conducted after the last active treated subject completes their 3-month follow-up. The number of complications per 1000 patient days will be estimated by Poisson regression model with only the intercept term, and the estimate and 95% CI will be provided using the Wald method, and the p-value comparing to the PG will be calculated by a Chi-square test.

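### The SAP runs the primary test on mITT, not the protocol's ITT set of all placed catheters; this selects on reaching a first dialysis session and may drop early complications

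*SAP*

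**What the plan says.** **Protocol.** Section 10.5 states: "The analyses of the primary endpoint will be based on the ITT population and repeated with per-protocol population as sensitivity analyses". Table 5 in section 10.3 gives ITT three conditions: consent, eligibility and placement of the catheter ("met all inclusion/exclusion criteria, and the Pristine™ Catheter was placed"). No dialysis session is required. Section 10.6 also summarises the secondary endpoints "using the ITT population". The protocol defines no mITT population.

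**SAP.** Section 5.2.1 says of the primary endpoint: "The analysis will be performed on the mITT population and repeated with per-protocol population as sensitivity analyses". Section 5.2.2 repeats it: "The analyses of the primary endpoint will be based on the mITT population and repeated with per-protocol population as sensitivity analyses". Table 2 in section 4.1 widens ITT to everyone whose procedure was initiated and splits it into three disposition groups: no device inserted, "Device inserted but subject did not undergo first dialysis session", and treated. Only the treated group forms mITT, and the per-protocol set is drawn from within mITT.

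The SAP gives no reason for the change, and its revision history shows only the original issue.

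**The concern.** The two documents name different populations for the single confirmatory test of a single-arm, open-label study. The SAP's set is also conditioned on the future. SAP 5.2.1 starts both the event count and the patient-days at the index procedure, but a patient enters the analysis only on reaching a later milestone, the first dialysis session. Thrombosis, migration or infection soon after placement can be the reason that session never happened. If so, both the event and the days disappear, while patients who do reach dialysis keep their pre-dialysis days.

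At stake are the agreement of the primary analysis with the protocol and the completeness of a complication rate that Protocol section 3 says is meant for the labeling.

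**Working it through.** **1. Which patients differ.**

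| Group on the disposition form | Protocol ITT | SAP ITT | SAP mITT |
|---|---|---|---|
| Eligible, device not inserted | no | yes | no |
| Inserted, no first dialysis session | yes, if inserted means placed | yes | **no** |
| Treated with the device | yes | yes | yes |

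No SAP population equals the protocol's ITT. The SAP's ITT is too wide and its mITT too narrow. The closest match is the second group plus the third. The protocol's own definition of a treated participant (Appendix A) asks for introduction and procedure success, not a dialysis session, so it does not support the exclusion either.

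**2. The plan's own figure.** Inputs from Protocol 10.2: goal λ0 = 0.0365 per day, assumed rate λ1 = 0.0315, one-sided α = 0.025, power 0.80, attrition 15%.
- Score formula: T = [(1.960·√0.0365 + 0.842·√0.0315) / 0.005]² = 10,976 days. Then 10,976 / 0.85 = 12,913 days, or 144 patients at 90 days. The plan states 12,765 days and 142.
- Exact Poisson: 12,765 × 0.85 = 10,850 days gives 80.3% power for non-inferiority and 85.5% for superiority (31.5 against 26.5).

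The plan's figures reproduce, with 12,765 as the attrition-inflated exposure. The choice of population does not alter them.

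**3. Size of the effect, on assumptions.** The documents give no count of inserted-but-never-dialysed patients. Assume k of them, each with exactly one countable event and d = 1 to 7 days of exposure, beside T = 10,850 to 12,765 mITT days.
- Rate in all placed patients when mITT runs at 31.5: (0.0315·T + k) / (T + k·d). For k = 3, d = 1, T = 10,850: 344.775 / 10,853 = 31.77 per 1000.
- Chance that the mITT test succeeds when the all-placed rate is exactly 36.5: P(X ≤ c), with X Poisson of mean 0.0365·(T + k·d) − k, where c = 357 at 10,850 days and 423 at 12,765 days.

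| k | Rise over 31.5 per 1000 | Relative | Chance of false success |
|---|---|---|---|
| 0 | 0 | 0 | 2.3–2.5% |
| 1 | 0.06–0.09 | 0.2–0.3% | 2.5–2.8% |
| 3 | 0.18–0.27 | 0.6–0.9% | 3.0–3.5% |
| 7 | 0.43–0.62 | 1.4–2.0% | 4.0–5.2% |
| 14 | 0.85–1.25 | 2.7–4.0% | 6.6–9.9% |

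**4. The opposite direction.** Restoring a patient raises the rate only if that patient's own rate exceeds it. At 31.5 per 1000, one event offsets 1000 / 31.5 ≈ 32 days. Three restored patients with 7 days each and no countable event would lower the rate: 341.775 / 10,871 = 31.44 per 1000, a fall of 0.06.

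**5. Pass or fail.** At the planning rate the expected count is 0.0315 × 10,850 ≈ 342 against a limit of 357, or 0.0315 × 12,765 ≈ 402 against 423. Restoring k events can reverse a pass only if the mITT count already lies within k of the limit.

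**The case against.** The conflict in wording cannot be argued away. SAP 4.1 does allow ITT where applicable, but 5.2.1 and 5.2.2 name only mITT and per-protocol for the primary endpoint. The objections concern consequence, and most of them stand.

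- **A reader might infer that the SAP removes the earliest device failures and so favours the device.** The documents do not show this. Death, withdrawal or a change of modality can also prevent a first session. A catheter that failed early, was corrected and was then used stays in mITT. Under SAP 5.2.1 an event counts only if it is device-related and either infectious or followed by a re-intervention. Excluded patients without such an event would pull the rate down if restored, so their exclusion works against the device.
- **A reader might infer a large relative understatement by supposing an observed rate far below plan.** The documents give no basis for choosing such a rate, and one event in every excluded patient is an extreme assumption. Both versions of the rate would then lie well below 36.5.
- **These patients are not lost to safety reporting.** The SAP uses ITT for adverse event summaries (section 7), for related adverse events through 1 month (5.3.2) and for technical success (5.3.3). The gap is in the primary rate.
- **Inserted may not mean exactly placed.** Protocol 7.4.1 distinguishes introduction without procedure success, so the mapping between the two documents is close rather than proven.

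What remains is an unexplained departure from the protocol's primary set, with selection on a post-placement event.

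**Conclusion.** The point holds as a protocol–SAP conflict on the primary analysis set. The SAP's choice conditions on a post-placement milestone and may remove early device-related complications; it keeps no analysis in the protocol's set against which to check this. The size and sign of any bias are unknown. With a few such patients, one event each and a rate near 31.5, the effect is about 1% or less, and the result probably would not change. It becomes material to the error rate only at about seven or more patients who all had a countable event, a number for which the documents offer no evidence. The reason to settle it is that the set behind the primary test should be fixed and consistent before the results are seen.

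**What to change.** Before the 3-month analysis:

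1. Make the primary set all eligible, consented participants with the catheter placed, as in the protocol. In SAP terms this is closest to the inserted-without-first-dialysis group plus the treated group. State how inserted maps to placed.
2. Use one ITT definition in both documents, and reconcile the secondary endpoints that Protocol 10.6 assigns to ITT and SAP 5.3 mostly runs on mITT.
3. Keep mITT and per-protocol as sensitivity analyses.
4. State when exposure ends for patients without procedure success, whose data Protocol 7.4.1 limits to 30 days. Otherwise the SAP's default for a missed 3-month visit could credit them with 105 days unless a discontinuation date is recorded. This 30-day limit does not cover patients with procedure success who simply never dialysed; they fall under ordinary follow-up (Protocol 7.5).
5. Report the number, reasons and events of patients outside mITT.

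The cost is SAP wording, a population flag, an exposure rule and one more run of the primary table. The sample size is unaffected, and Protocol section 5 already sets the enrollment target of 142 in terms of successful placements.

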#### Infectious Complications

Complications due to any documented diagnosis of access infection requiring medical intervention (managed in an outpatient or inpatient setting) or sepsis as diagnosis in the hospitalization file whether access related or not.

Subject will be considered as having an infectious complication and will be counted as an event if the subject has experienced a device-related infection prior to the subject's end day of investigation period:

- **AE CRF Page:** Start Date of AE ≤ End Day of Investigation period **AND** Relationship to study Device: Equals 'Related' or 'Likely Related' **AND** Was event infectious: Equals Yes; subject will be considered as a failure at AE start date

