#### Non-infectious complications

Complication due to any noninfectious cause (thrombosis of the access, fibrin material within or around a catheter, catheter migration, central vein stenosis or thrombosis) requiring a revision procedure to maintain patency or improve access performance (i.e., thrombolysis, angioplasty, or surgical correction) in an inpatient or outpatient setting or removal or abandonment with creation of a new access that was not due to an access-related infection.

Subject will be considered as having a non-infectious complication and will be counted as an event if the subject has experienced a device-related non-infectious AE resulting in a re-intervention prior to the subject's end day of investigation period:

- **AE CRF Page:** Start Date of AE  $\leq$  End Day of Investigation period **AND** Relationship to study Device: Equals 'Related' or 'Likely Related' **AND** Was event infectious: Equals No **AND** Did AE Result in a Catheter Re-Intervention: Equals Yes; subject will be considered as a failure at AE start date

For each subject, the number of complications through the investigational duration is estimated as:

$$((\text{Number of observed infectious complications} + \text{Number of observed non-infectious complications}) * 1000) / \text{Length of investigation duration (Days)}$$

Length of investigation duration (Days) is from the date of index procedure to the end day of each subject's investigation period (End day of investigation period – Date of index procedure + 1); the end day of investigational period will be the earliest occurrence date of the following three events:

- If a subject's Pristine™ Catheter is removed due to Kidney Transplant, Transferred to AVG/AVF, Peritoneal Dialysis, Withdrawal of Care, or Other reasons, then the date of removal will be used to calculate the length of investigation duration. That is:
  - **Hemodialysis Catheter Re-Interventions CRF page:** Catheter removal Equals Yes **AND** Reason for catheter removal Equals: Kidney Transplant, Transferred to AVG/AVF, Peritoneal Dialysis, Withdrawal of Care, or Other; date of re-intervention is used in the estimation of investigation duration

$$\text{Length of investigation duration (Days)} = \text{Removal date} - \text{date of index procedure} + 1$$

- If a subject discontinues early, then the discontinuation date will be used to calculate the length of investigation duration.
 

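### SAP 5.2.2 gives a rate built from repeat events a Poisson variance, so near the performance goal the one-sided error exceeds 0.025 if patients differ in risk

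*SAP*

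**What the plan says.** **Counting (SAP 5.2.1).** The formula begins "For each subject, the number of complications through the investigational duration is estimated as" and takes the observed infectious plus non-infectious complications, times 1000, over that subject's days. The event rules in the same section read differently. An infection "will be counted as an event if the subject has experienced a device-related infection", and the "subject will be considered as a failure at AE start date". The rule for non-infectious events has the same form.

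**Testing (SAP 5.2.2).** First, "A one-sided p-value will be derived based on a Poisson distribution", with success below 0.025. The closing sentence then reads "The number of complications per 1000 patient days will be estimated by Poisson regression model with only the intercept term", says that "the estimate and 95% CI will be provided using the Wald method", and adds that "the p-value comparing to the PG will be calculated by a Chi-square test". It does not say which p-value decides, or give the chi-square a direction.

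**Protocol.** Section 10.5 says "A one-sided p-value will be derived based on an Poisson distribution", and the synopsis says the same.

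**What is absent.** Neither document mentions overdispersion, a scale parameter, robust variance or a subject-level term. The only sensitivity analysis stated for the primary endpoint is the per-protocol repeat, which keeps the same variance. The SAP appendices are listed by title only, so a dispersion rule there cannot be excluded.

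**The concern.** A Poisson variance equals the mean. That is right for a total of repeat events only if all patients share one underlying rate. If some patients are more prone to infection or thrombosis than others, the total varies more than the Poisson model allows. The test then rejects too easily near the PG, and the interval is too narrow there.

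The effect grows with the number of events per patient, and this PG implies several. A non-inferiority claim could be accepted too often if the true rate were near 36.5. SAP 1.2 says the results are meant for the device labelling, so the interval matters as well as the verdict.

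**Working it through.** **1. Reproduce the plan's figure (SAP 2.4).** Inputs: PG 36.5 and planning rate 31.5 per 1000 days, one-sided 0.025, power 80%, attrition 15%, 12,765 days, 142 participants.

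- 12,765 × 0.85 = 10,850 days, so 10,850 × 0.0365 = 396.0 events are expected at the PG.
- The exact Poisson test passes at 357 events or fewer, with error 0.0250 and power 0.803 at 31.5.
- 10,850 / 0.85 = 12,765 days, and 12,765 / 90 = 141.8, that is 142.

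The stated size is reproduced, with variance equal to mean.

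**2. Effect of patients who differ.** Let patient rates have relative variance θ (gamma). The documents give no θ, so 0.05 to 1.0 is an assumed range. The variance of the total is inflated by 1 + θμ, where μ is the mean count per patient. With 121 patients over 10,850 days, μ = 396.0 / 121 = 3.27 at the PG. The approximate error is Φ(−1.96 / √(1 + 3.27θ)). Approximate Wald coverage at 31.5 is 2Φ(1.96 / √(1 + 2.835θ)) − 1, since 31.5 × 90 / 1000 = 2.835.

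Error below is at 36.5; coverage and power are at 31.5. The simulated columns use 121 patients and 10,850 days. The Poisson column shows the range over two sets of 20,000 trials.

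| θ (assumed) | Poisson error, simulated | Poisson error, formula | Unhalved chi-square error | Robust error | Wald 95% coverage | Robust power |
|---|---|---|---|---|---|---|
| 0 | 0.026–0.027 | 0.025 | 0.012 | 0.027 | 0.95 | 0.80 |
| 0.05 | 0.034–0.035 | 0.035 | 0.017 | 0.025 | 0.93 | 0.74 |
| 0.1 | 0.044–0.045 | 0.044 | 0.024 | 0.026 | 0.92 | 0.68 |
| 0.25 | 0.070–0.072 | 0.073 | 0.045 | 0.025 | 0.87 | 0.56 |
| 0.5 | 0.112–0.116 | 0.114 | 0.084 | 0.028 | 0.80 | 0.43 |
| 1.0 | 0.175–0.184 | 0.172 | 0.144 | 0.033 | 0.69 | 0.30 |

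The first two coverage values come from the formula and the others from simulation. The one-sided Wald test has the same cutoff (357) as the exact test. The chi-square p-value taken without halving passes at 351 or fewer, with error 0.012 and power 0.70 under a pure Poisson model.

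**3. Other exposure patterns.** With 142 patients of 90 days, the Poisson error is 0.044, 0.072, 0.115 and 0.175 at θ = 0.1, 0.25, 0.5 and 1.0. With 15% leaving at a uniform time, it is 0.069, 0.109 and 0.170 at 0.25, 0.5 and 1.0.

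**4. Which count is meant.** At most one infectious and one non-infectious event per subject gives at most 2 × 142 = 284 events. On 10,850 days that is 284 / 10.85 = 26.2 per 1000, below the limit of 357 events, so the test could not fail. The same holds for any total exposure of at least 8,741 days (61.6 per subject). A PG of 36.5 is meaningful only if repeat events count.

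**5. Low rates.** In the feasibility study (SAP 1.1), 90.9% patency among 44 catheters implies 4 losses, and there were 6 device-related infections. Treating these as 10 qualifying events over an assumed 7,110 to 7,920 catheter-days gives 10 / 7.92 = 1.3 to 10 / 7.11 = 1.4 per 1000. At 1.35 per 1000, simulated coverage of the planned Wald interval is 0.964, 0.965, 0.960 and 0.951 at θ = 0, 0.25, 0.5 and 1.0. At 3 per 1000 and θ = 1.0 it is 0.919.

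**The case against.** **The count is unsettled.** If each subject contributes at most one event of each type, counts are bounded. A check over assumed event probabilities gave a variance-to-mean ratio of 0.32 to 0.88, so the Poisson interval would be too wide. This stands as a reason to settle the counting rule first. It does not rescue the plan, because under that reading the test could not fail.

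**The larger figures rest on assumptions.** No document gives a variance. The simulation also lets events recur without ending exposure, whereas catheter removal can be a qualifying event and protocol 7.5 keeps participants in the study only until removal. If an assumed 10%, 25% or 50% of events end follow-up, with the rate held at 36.5, the error at θ = 1.0 falls from 0.172 to 0.141, 0.120 and 0.093. At θ = 0.25 it falls from 0.075 to 0.061, 0.051 and 0.043. The error is still inflated, but the table shows the upper end.

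**The chi-square may be the decision rule.** Read without halving, it exceeds 0.025 only above a variance of about 0.1. This stands, so the inflation does not apply equally to every p-value named.

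**Other remedies exist.** A negative binomial or scaled Poisson model would also address the point, and a robust sensitivity analysis would leave the primary test alone. The last option leaves the decision on the Poisson variance.

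A reader might infer that the trial's conclusion is unsafe, or that the interval is too narrow whatever the rate. The documents do not support either. The excess error arises near the PG, and at 1 to 3 per 1000 the verdict is the same under either variance.

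**Conclusion.** The point holds, conditionally. If repeat events count, patients differ in risk and the true rate is near 36.5, the one-sided Poisson test exceeds 0.025. On 10,850 days the error runs from about 0.035 to 0.18 across the assumed variances. The direction holds for any variance above zero. With no variation between patients, the planned test holds its level.

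At the planning rate of 31.5, coverage of the 95% Wald interval falls to about 0.92, 0.87, 0.80 and 0.69 at variance 0.1, 0.25, 0.5 and 1.0. The argument about the interval therefore rests on the sponsor's own planning rate, not on the rate that the feasibility data suggest. The change should be made before the 3-month analysis, so that the variance is not chosen after the data are seen.

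**What to change.** 1. **SAP 5.2.1.** State that every qualifying event counts, and reconcile the failure and counted-once wording with the formula. Do this first, because the rest depends on it.
2. **SAP 5.2.2.** Replace both the sentence on the Poisson p-value and the closing sentence with one rule, deleting the unlinked chi-square:

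> Subject counts of complications are analysed by Poisson regression with log(days) as offset and subject-level robust variance. The one-sided p-value is the lower-tail probability of z = (intercept − log(PG/1000)) / robust SE. Success requires p < 0.025, equivalent to the upper limit of the two-sided 95% CI from the same robust SE lying below the PG. The exact Poisson test on total events and total days is a sensitivity analysis.

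3. **Protocol 10.5 and synopsis.** Record the change and align the wording. Also reconcile the superiority PG, which is 26.5 in SAP 5.2.2 but 31.5 in protocol 10.5 and SAP 2.4, before applying the same rule to that step.
4. **SAP 2.4.** State that 80% power assumes no overdispersion.

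**Cost.** Text, a few lines of SAS and a recorded protocol change, with no new data. If patients differ, the interval is wider and power at 31.5 falls from about 0.80 to 0.74, 0.68, 0.56, 0.43 and 0.30 at variance 0.05, 0.1, 0.25, 0.5 and 1.0. Robust error is 0.024 to 0.033, close to 0.025 but not exact.
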